#### **11.10. Relationship to Investigational Product**

The investigator is obligated to assess the relationship between study treatment and each occurrence of each AE/SAE.

There may be situations in which an SAE has occurred, and the investigator has minimal information to include in the initial report to the Sponsor. However, it is very important that the investigator always assesses causality for every event before the initial transmission of the SAE data to the Sponsor.

The investigator may change his/her opinion of causality in light of follow-up information and send a SAE follow-up report with the updated causality assessment.

The following classifications should be used when evaluating the relationship of AEs or SAEs to study treatment.

**Table 4: Adverse Event Relationships**

Relationship	Definition
Unrelated	No relationship between the AE and the administration of study treatment; the AE can be explained by other etiologies such as concomitant medications or subject's clinical state.

Relationship	Definition
Possibly related	A reaction that follows a plausible temporal sequence from administration of the study treatment, has a biologically causal relationship with the study treatment, or for which an alternative explanation for the AE is lacking. The reaction might have been produced by the subject's clinical state or other modes of therapy administered to the subject.
Probably related	A reaction that follows a plausible temporal sequence from administration of the study treatment and has a biologically causal relationship with the study treatment, and the influence of alternative factors for the AE is unlikely.

## 11.11. Severity Assessment

For purposes of consistency, if required the investigator may use the intensity grades presented in [Table 5](#).

**Table 5:** Adverse Event Intensity Grades

Grade	Definition
Mild	Does not interfere with subject's usual function and activities.
Moderate	Interferes to some extent with subject's usual function and activities.
Severe	Interferes significantly with subject's usual function and activities.

To ensure there is no confusion or misunderstanding of the difference between the terms “serious” and “severe,” which are not synonymous, the following note of clarification is provided:

The term “severe” is used to describe the intensity of a specific event (as in mild, moderate, or severe myocardial infarction). The event itself, however, may be of relatively minor medical importance (such as a severe headache). This is not the same as “serious,” which is based on the subject/event outcome or action criteria usually associated with events that pose a threat to a subject’s life or functioning. Seriousness (not severity) serves as a guide for defining regulatory reporting obligations.

If an AE increases in severity (eg, from moderate to severe); decreases in severity (eg, changes from moderate to mild); or if there is a change in seriousness, a new AE will be opened and the original AE will be closed. If an AE is still ongoing at the time of a subject’s completion of the last study follow-up visit, the resolution/stop date and time is left blank.

## 11.12. Recording and Reporting Adverse Events

Adverse events will be recorded starting at the signing of the informed consent form (ICF) and will be followed by the investigator until the AE is resolved or stabilized. All study site follow-up should be documented.

Adverse events, AESIs, and SAEs will be reported from execution of the ICF through completion of study participation. The investigator is required to record the AE, regardless of the severity of the event or its relationship to study treatment.

The investigator will attempt to establish a diagnosis of the event based on signs, symptoms, and/or other clinical information. Whenever possible, the diagnosis (not the individual signs/symptoms) will be documented as the AE/SAE.

The investigator must follow all AEs until the event has resolved or stabilized or at such time, the investigator refers the subject to a non-study physician. The investigator will document further all of the follow-up information in the subject's source documents.

The investigator is responsible for reporting all AEs as presented in [Table 6](#).

**Table 6: Reporting Requirements for Adverse Events**

Category	Reporting Time	Type of Report
Serious adverse events, and AESIs	Within 24 hours of first knowledge of event	Initial report on the SAE/AESI Form, appropriate eCRF, and source document
	Within 24 hours of receipt of follow-up information	Follow up report on the Follow-up SAE/AESI Form, appropriate eCRF, and source document
Nonserious adverse events	Per case report form submission procedure	Appropriate eCRF and source document

AESI = adverse event of special interest; eCRF = electronic case report form; SAE = serious adverse event.

It is **not** acceptable for the investigator to send photocopies of the participant's medical records to the Sponsor in lieu of completion of the SAE report form.

There may be instances when copies of medical records for certain cases are requested by the Sponsor. In this case, all participant identifiers, with the exception of the participant number, will be redacted on the copies of the medical records before submission to an agency.

### 11.13. Pregnancy Reporting

If a female subject, or the female partner of a male subject, becomes pregnant during the study, the investigator will report to the Sponsor as soon as she/he becomes knowledgeable of the pregnancy. The subject will be followed for the duration of the pregnancy and the outcome (eg, spontaneous abortion, live birth, still birth, congenital anomalies, birth defects) will be reported to the Sponsor as soon as it is known. If the pregnancy results in a live birth, a postdelivery follow-up will be performed at least 28 days after the baby is born and must be reported to the Sponsor's pharmacovigilance personnel, or designee, within 24 hours of the study site becoming aware of the follow-up information.

Information including the definition of Woman of Childbearing Potential (WOCBP), Contraceptive Guidance, and Collection of Pregnancy Information can be found in [Appendix 3](#).

## 12. STATISTICAL CONSIDERATIONS

### 12.1. Sample Size Determination

Approximately 50 subjects will be enrolled into one of two age cohorts: up to 40 subjects in 2 to  $\leq$  12 years cohort or up to 10 subjects in 12 to  $\leq$  17 years.

An overall sample size of 50 subjects will provide greater than 90% power to determine that at least 50% of the subjects achieve confirmed complete closure of all StrataGraft treatment sites on or before Week 12 without autograft placement, assuming that the actual proportion of subjects with confirmed complete closure of all StrataGraft treatment sites without autografting will be  $\geq$  83%. This assumption is based upon the results of a study in adults for the same indication ([Holmes, 2020](#)).

Similar power is provided with the 40-subject sample of the 2 to  $\leq$  12 years cohort, which is considered to be the more common group to be enrolled. In the event that the 40 subjects have been enrolled into the 2 to  $\leq$  12 years cohort but the enrollment into the older 12 to  $\leq$  17 years cohort is not yet complete, the Sponsor reserves the right to close the study at their discretion.

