## 4.2. Study Rationale

StrataGraft is under development by Stratatech Corporation, a Mallinckrodt Company, as an alternative to autografting to promote the healing of acute thermal burns. A Biologics License Application for StrataGraft for the treatment of adults with thermal burns containing intact dermal elements for which surgical intervention is clinically indicated (DPT burns) has received Food and Drug Administration (FDA) approval. Data from a Phase 3 study in adults demonstrated that 83% of wounds treated with a single application of StrataGraft achieved durable closure at Month 3 without autografting (Holmes, 2020). For that study, durable wound closure was defined as closure at 2 consecutive visits at least 2 weeks, but not more than 5 months apart and including or encompassing the Month 3 time point. Subjects with missing data were considered to have failed the endpoint.

Treating DPT burns with StrataGraft rather than autografting may be particularly beneficial for pediatric burn patients. This study is being conducted in order to evaluate the safety and efficacy of StrataGraft treatment in pediatric subjects with DPT burn injuries.

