#### 12.3.1. Efficacy Analyses

##### 12.3.1.1. Primary Endpoint

The pediatric study plans to enroll up to 50 subjects into two age cohorts: 2 to  $\leq$  12 years and 12 to  $\leq$  17 years. Endpoints will be assessed using the entire ITT population.

The primary efficacy endpoint for this study the percentage of subjects achieving confirmed complete closure of all StrataGraft treatment sites on or before Week 12 without autograft placement. For subjects with more than one treatment site, all treatment sites must be confirmed closed before the subject can be declared to be confirmed closed. Confirmed complete wound closure is defined as complete skin re-epithelialization confirmed at 2 consecutive visits at least 2 weeks apart but no later than Week 20. Complete confirmed wound closure will be considered to have occurred at the earlier of the two observations of complete skin re-epithelialization without drainage.

For the primary efficacy endpoint, number (%) and 95% Confidence Interval (CI) derived from the normal approximation to the binomial will be summarized based on the ITT population. Subjects with missing data will be imputed as non-responders. The statistical significance for the primary endpoint is declared if the lower limit of the 95% CI of the endpoint is  $\geq 50\%$ .

The analysis will also be performed based on all observed data, i.e, excluding any missing data. The analyses by age cohort will be presented.

The Objective, Population, Hypothesis, Endpoint, and Intercurrent Events and Data Handling for the Primary Endpoint are described in [Table 7](#).

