To evaluate whether StrataGraft treatment eliminates or reduces the need for autografting and promotes wound closure in a pediatric population with thermal burns that contain intact dermal elements and for which autografting is clinically indicated.	All enrolled subjects who received StrataGraft	$H_0$ : The response rate of primary endpoint is less than or equal to the 50% $H_1$ : The response rate of the primary endpoint is greater than the 50%  Positive study criteria: The lower bound of primary endpoint 95% CI derived from the normal approximation to the binomial $> 50\%$ .	Percentage of subjects achieving confirmed complete closure of all StrataGraft treatment sites on or before Week 12 without autograft placement. Confirmed complete wound closure is defined as 100% re-epithelialization confirmed at 2 visits at least 2 weeks apart but before Week 20.	Early discontinuation due to: 
 
• Withdrawal of informed consent
 
• Lost to follow-up
 
• Adverse event
 
• Investigator decision
 
• Death
 
• Other
 
 Missing/incomplete data will be imputed as failure (ie, no confirmed complete wound closure).

CI = Confidence Interval; LB = Lower Bound

**Table 8: The Objective, Population, Hypotheses, Endpoints and Intercurrent Events and Data Handling for Ranked Secondary Efficacy Endpoints**

Objectives	Population	Hypotheses	Endpoints	Intercurrent events and data handling
To evaluate the mean averaged percent of wound area closure of StrataGraft treatment site without autograft placement at Week 12	All enrolled subjects who received StrataGraft	$H_{01}$ : Mean of averaged percent wound area closure of StrataGraft treatment site without autograft placement at Week 12 $\leq 50\%$ $H_{11}$ : Mean percent of wound area closure of StrataGraft treatment site without autograft placement at Week 12 $> 50\%$	Mean of averaged percent area of StrataGraft treatment site closed without autograft placement at Week 12	
Early discontinuation due to:
 
 
• Withdrawal of informed consent
 
• Lost to follow-up
 
• Adverse event
 
• Investigator decision
 
• Death
 
• Other
 
 
Missing/incomplete continuous variables will not be imputed.

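### Does the power claim fail because an adult per-wound closure rate is used as the rate at which a child closes every treated site?

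*Combined protocol and SAP*

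**What the plan says.** The claim in protocol Section 12.1 reads "An overall sample size of 50 subjects will provide greater than 90% power to determine that at least 50% of the subjects" reach the primary endpoint, "assuming that the actual proportion of subjects with confirmed complete closure of all StrataGraft treatment sites without autografting will be" at least 83%. On the source of the 83% it says "This assumption is based upon the results of a study in adults for the same indication". It adds "Similar power is provided with the 40-subject sample" planned for the younger cohort, and lets the sponsor close the study once that cohort is full.

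Section 4.2 describes the adult result as "83% of wounds treated with a single application of StrataGraft achieved durable closure at Month 3 without autografting".

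The primary endpoint is judged per child. Section 12.3.1.1 requires that "all treatment sites must be confirmed closed before the subject can be declared to be confirmed closed", and inclusion criterion 7 in Section 7.1 allows as many as three separate areas on one limb or one plane of the torso. Success means a normal-approximation 95% confidence interval whose lower limit is at least 50%. The second ranked secondary endpoint (Section 12.3.1.2) counts closure per site.

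**The concern.** Closing every site is harder than closing one. If 83% is the chance that a given wound closes, a child with two or three sites has a lower chance of closing all of them unless the sites always agree. On that reading, Section 12.1 takes as a minimum for subjects a figure that its source supports only for wounds.

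The power statement is the only quantitative support for 50 subjects and for the option to stop at 40. If the true all-sites rate were near 70%, the design would miss its stated power, and a failed primary result might reflect the all-sites rule rather than the product.

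**Working it through.** **Inputs from the protocol.** n = 50 or 40, null rate 50% and assumed rate 83% (Section 12.1 and Table 7); normal-approximation 95% interval with lower limit at least 50% (Section 12.3.1.1); one to three sites per child (Section 7.1).

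**Inputs not in the documents, so assumed below.** The mix of one-, two- and three-site children, the correlation of closure within a child, and 83% as the chance for each site whatever the number of sites.

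**Step 1: responders needed.** Lower limit = p − 1.96 × √(p(1 − p)/n).
- n = 50: 32/50 gives 0.640 − 0.133 = 0.507 (success); 31/50 gives 0.620 − 0.135 = 0.485 (failure).
- n = 40: 26/40 gives 0.650 − 0.148 = 0.502 (success); 25/40 gives 0.625 − 0.150 = 0.475 (failure).

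**Step 2: the plan's own figure.** Exact binomial power at 83%:
- P(X ≥ 32 | n = 50) = 99.97%
- P(X ≥ 26 | n = 40) = 99.84%

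Both statements in Section 12.1 reproduce, with much to spare.

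**Step 3: the lowest rate that still gives 90% power.** Solving the same tail probabilities for 90% gives 0.713 (n = 50) and 0.729 (n = 40). The subject-level rate can fall about 12 or 10 percentage points below 83% first.

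**Step 4: treat 83% as a per-site rate with independent sites.** P(all sites close) is 0.83 for one site, 0.83² = 0.689 for two and 0.83³ = 0.572 for three.

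| Share with 1 / 2 / 3 sites | Subject-level rate | Power, n = 50 | Power, n = 40 |
|---|---|---|---|
| 60 / 25 / 15% | 75.6% | 97.7% | 95.5% |
| 50 / 25 / 25% | 73.0% | 94.1% | 90.4% |
| equal thirds | 69.7% | 84.8% | 79.5% |
| all two sites | 68.9% | 81.7% | 76.2% |
| all three sites | 57.2% | 20.3% | 20.1% |

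**Step 5: how many multi-site children break the claim?** Suppose all other children have one site.
- n = 50, two-site: (0.830 − 0.713)/(0.830 − 0.689) ≈ 83%
- n = 50, three-site: (0.830 − 0.713)/(0.830 − 0.572) ≈ 45%
- n = 40: about 72% two-site or 39% three-site

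**Step 6: let sites within a child agree to some degree.** In a beta-binomial model with intraclass correlation ρ, P(two close) = 0.83 × [0.83(1 − ρ) + ρ]. At ρ = 0.2 this is 0.83 × 0.864 = 0.717, and P(three close) is 0.636. Equal thirds then gives (0.830 + 0.717 + 0.636)/3 = 72.8%, with power 93.6% (n = 50) and 89.8% (n = 40). At ρ = 0.5, even an all-three-site population gives 91.0% at n = 50, though 86.5% at n = 40.

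**Step 7: is the wound rate really a ceiling?** Not in general. Suppose nine one-site children all close and one three-site child closes none. The wound rate is 9/12 = 75%, while the subject rate is 9/10 = 90%. A pooled wound rate gives more weight to children with more sites, so it caps the all-sites rate only if closure per site does not vary with the number of sites. The documents do not address that.

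**The case for a change.** The strongest case for a change is that the protocol itself separates the two units, with a per-subject primary endpoint and a per-site secondary one, and then sizes the first with a figure reported for wounds. The adult figure of more than 95% of subjects in Section 6.2 does not settle this, because that closure is not described as durable or confirmed and Section 12.1 does not use it. The 40-subject option also has less room: with equal thirds and ρ = 0.2 it sits just under 90%. With an exact binomial interval in place of the planned one, 33/50 or 27/40 would be needed, and the break-even rates would rise to 0.731 and 0.751. The 50/25/25 mix would then give 89.7% and 83.3%.

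The missing explanation stands, and so does the thinner margin at 40. A shortfall is not shown. The low-power rows rest on site mixes that appear nowhere in the documents, and three sites is a permitted maximum, not an expectation. A child's sites share the patient and must lie on one limb or one plane of the torso, so full independence is the pessimistic extreme. The documents do not say how many wounds each adult contributed; if it was one, 83% is already a per-patient rate for one-site patients. The adult definition also differed, since closure had to include or span Month 3, whereas here closure first seen at any time up to Week 12 counts once confirmed.

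**Conclusion.** No change follows. Section 12.1 states a conditional claim on the correct unit, and that claim is true with wide headroom: 99.97% and 99.84% against a stated 90%. Only the link to the adult source is loose. Under the planned interval, the claim would fail only if the true all-sites rate were below about 0.713 (n = 50) or 0.729 (n = 40). With 83% per site, unaffected by the number of sites, that requires multi-site children to make up a large share (at n = 50 about 83% with two sites or 45% with three; at n = 40 about 72% or 39%; the rest single-site) and closure within a child to be close to independent.

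An added explanation or sensitivity range would document the assumption without altering the sample size, the success rule or any analysis. If the primary endpoint failed because of the all-sites rule, the per-site secondary endpoint would show it, at least descriptively. The SAP memo also records that enrolment closed with one subject and that no formal analyses will be done, so the point touches the design rationale and no result.

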### 12.2. Analysis Populations

The Intent-to-Treat (ITT) and Safety populations will include all enrolled subjects who received StrataGraft.

### 12.3. Statistical Analyses

This section provides a general summary of the statistical methods to be used in analyzing study data. A more detailed statistical analysis plan (SAP) will be provided in a separate document that will be finalized prior to database lock. SAS version 9.4 or newer will be used.

Descriptive statistics for continuous variables will include the mean, median, standard deviation, minimum value, and maximum value. Categorical data will be summarized by counts and percentages.

#### 12.3.1. Efficacy Analyses

##### 12.3.1.1. Primary Endpoint

The pediatric study plans to enroll up to 50 subjects into two age cohorts: 2 to  $\leq$  12 years and 12 to  $\leq$  17 years. Endpoints will be assessed using the entire ITT population.

The primary efficacy endpoint for this study the percentage of subjects achieving confirmed complete closure of all StrataGraft treatment sites on or before Week 12 without autograft placement. For subjects with more than one treatment site, all treatment sites must be confirmed closed before the subject can be declared to be confirmed closed. Confirmed complete wound closure is defined as complete skin re-epithelialization confirmed at 2 consecutive visits at least 2 weeks apart but no later than Week 20. Complete confirmed wound closure will be considered to have occurred at the earlier of the two observations of complete skin re-epithelialization without drainage.

For the primary efficacy endpoint, number (%) and 95% Confidence Interval (CI) derived from the normal approximation to the binomial will be summarized based on the ITT population. Subjects with missing data will be imputed as non-responders. The statistical significance for the primary endpoint is declared if the lower limit of the 95% CI of the endpoint is  $\geq 50\%$ .

The analysis will also be performed based on all observed data, i.e, excluding any missing data. The analyses by age cohort will be presented.

The Objective, Population, Hypothesis, Endpoint, and Intercurrent Events and Data Handling for the Primary Endpoint are described in [Table 7](#).

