**Re: MNK15011001 – Statistical Analysis Plan**

As of January 2024, the decision was made to close enrollment to the MNK15011001 study. Due to only 1 subject enrolled in the study, there will be no formal analyses performed on the study data. As such, this memo serves as the Statistical Analysis Plan (SAP).

Listings will be produced for all data collected from the eCRF and external laboratory transfers for subject [REDACTED]. No other outputs are planned.

A table of contents of the planned output is in the following table. The file name will be provided as the [text].pdf with corresponding program file [text].txt. Study Data Tabulation Model (SDTM) datasets will be provided as .sas7bdat and .xpt files with corresponding specifications as an Excel file. Per the sponsor, there will be no ADaM datasets, define.xml files, reviewer's guides, nor SDTM annotated eCRF required. All datasets, planned output, and corresponding SAS programs will be provided to the sponsor via Mallinckrodt Secure File Transfer Protocol (SFTP) and will not be filed in the eTMF.

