### 12.3.1.2. Ranked Secondary Endpoints

After the primary endpoint is successfully reached, the ranked secondary efficacy endpoints will each be tested with a 2-sided confidence interval with 0.05 Type I error in a hierarchical manner in the rank order as in [Table 8](#). The ranked secondary endpoints are:

1. Mean of averaged percent area of StrataGraft treatment site closed per subject at Week 12 without autograft placement
2. Number (%) of confirmed complete wound closures of the StrataGraft treatment sites on or before Week 12 without autograft placement
3. Mean of averaged percent area of StrataGraft treatment site autografted by Week 12

For continuous efficacy endpoints, missing data will not be imputed. Missing or incomplete binary variables will be imputed as failures. Missing data are anticipated to occur only if the subject is lost to follow-up because information can be obtained for a missing visit when the subject returns for a subsequent visit. If a subject has autograft placement, the data collected after the autograft placement will be censored.

The averaged percent area closed per subject at Week 12 will be calculated as (Sum of percent area closed across treatment sites for a subject at Week 12/the total number of treatment sites on a subject).

The percentage of StrataGraft treatment sites with confirmed complete wound closure on or before Week 12 will be calculated as [(Total number of StrataGraft treatment sites with confirmed complete wound closure without autografting on or before Week 12/Total number of treatment sites) x 100].

The averaged percent area of StrataGraft treatment sites per subject autografted by Week 12 will be calculated as (Sum of percent area of StrataGraft treatment sites per subject autografted by Week 12/the number of treatment sites on that subject). It is a cumulative sum of percent area autografted for all nonmissing visits on or before Week 12.

The summary statistics with 95% confidence interval (CI) and p-value based on null hypothesis specified in [Table 8](#) for each endpoint from t-distribution will be presented based on the ITT population by designated treatment site and pooled designated treatment site. The analyses by age cohort will be presented.

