### 12.3.1.3. Binary Endpoints

For binary endpoints, number (%) of subjects and its 95% CI derived from the normal approximation to the binomial will be summarized based on ITT by designated treatment site and pooled designated treatment site. The denominator for a treatment site is determined by numbers of subjects with the designated site. The number and percent of missing data will be shown.

The missing data of binary endpoints will not be imputed for exploratory endpoints.

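### The normal-approximation interval behind the primary success rule passes 32/50, a one-sided error of 3.25% against an implied 2.5%

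*Combined protocol and SAP*

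**What the plan says.** Section 12.3.1.1 of the protocol specifies "number (%) and 95% Confidence Interval (CI) derived from the normal approximation to the binomial will be summarized based on the ITT population" and declares significance if the lower limit is at least 50%. Table 7 sets a null response rate of 50% or less against an alternative above 50%. It bases a positive study on "The lower bound of primary endpoint 95% CI derived from the normal approximation to the binomial" lying strictly above 50%. The interval is therefore the decision rule as well as a summary.

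No Type I error is stated for the primary endpoint. Section 12.3.1.2 says the ranked secondaries, which open only after the primary succeeds, will "each be tested with a 2-sided confidence interval with 0.05 Type I error". Section 12.1 says "An overall sample size of 50 subjects will provide greater than 90% power" if the true rate is at least 83%. It also lets the sponsor close the study once 40 younger subjects are enrolled, even if the older cohort is incomplete. Section 12.3.1.3 uses the same method for the binary endpoints: "its 95% CI derived from the normal approximation to the binomial". No continuity correction or exact test is named.

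The SAP memo states that, with one subject enrolled, "there will be no formal analyses performed on the study data"; it plans listings only.

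**The concern.** The Wald interval takes its standard error from the observed proportion. When that proportion is above 50%, this standard error is smaller than the one that holds under the null, so the lower limit sits too high. Where the cut-off falls near the boundary, a result can be called positive although its exact 95% interval still contains 50%.

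At stake are the error rate of the single confirmatory criterion, the opening of the secondary hierarchy behind it, and the precision claimed for the reported lower limit.

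**Working it through.** **Inputs.** Planned total n = 50, assumed rate 83%, possible closure with 40 younger subjects (Section 12.1). Null rate 50% (Table 7). Two-sided 95% normal-approximation interval, with missing data counted as non-response so that the denominator stays at the ITT total (Section 12.3.1.1). Reference level 2.5% one-sided: comparing the lower limit of a two-sided 95% interval with a null value is a one-sided 2.5% test, and this agrees with the two-sided 0.05 in Section 12.3.1.2. It is an inference.

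**Cut-off at n = 50.** The Wald lower limit is p − 1.96·√(p(1−p)/n).
- 31/50: 0.62 − 1.96·√(0.62·0.38/50) = 0.485, fails.
- 32/50: 0.64 − 1.96·√(0.64·0.36/50) = 0.64 − 1.96·0.0679 = 0.507, passes.

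The cut-off is 32 whether the rule is read as at least 50% (Section 12.3.1.1) or above 50% (Table 7). The same holds at every total below.

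**The plan's own figure.** Power = P(X ≥ 32 | n = 50, p = 0.83) = 99.97%, so the stated power above 90% is reproduced.

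**Error at n = 50.** P(X ≥ 32 | n = 50, p = 0.5) = 3.25%, which is 0.75 percentage points above 2.5%. The exact (Clopper-Pearson) lower limit is 49.2% at 32/50 and 51.2% at 33/50. The exact rule therefore needs 33, with error 1.64% and power 99.90%.

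**Totals of 40 to 50.** For each total, take the smallest passing count x and then P(X ≥ x | p = 0.5):

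| Total | Wald cut-off | Wald error | Exact cut-off |
|---|---|---|---|
| 40 | 26 | 4.03% | 27 |
| 41 | 27 | 2.98% | 28 |
| 42 | 28 | 2.18% | 28 |
| 43 | 28 | 3.30% | 29 |
| 44 | 29 | 2.44% | 29 |
| 45 | 29 | 3.62% | 30 |
| 46 | 30 | 2.70% | 31 |
| 47 | 30 | 3.95% | 31 |
| 48 | 31 | 2.97% | 32 |
| 49 | 32 | 2.22% | 32 |
| 50 | 32 | 3.25% | 33 |

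The Wald rule exceeds 2.5% at 8 of the 11 totals and holds at 42, 44 and 49. The exact rule's error runs from 1.29% (total 46) to 2.44% (total 44). The 4.03% maximum applies at a total of 40, which under the early-closure option arises only if no older subject enters.

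**Reported precision at 83%, n = 50.** Summing binomial probabilities over all outcomes, Wald coverage is 92.6%, and the lower limit lies above the true rate 5.7% of the time. The exact interval gives 96.3% and 2.1%.

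**Other readings of normal approximation.** A Wilson score interval has a lower limit of 50.1% at 32/50, so it also passes, with the same 3.25%. A continuity-corrected Wald interval would move the cut-off to 33/50, but the protocol does not mention one.

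**The case against.** The strongest objection is that nothing remains to be fixed. The SAP memo closes the study with one subject and listings only, so no primary interval will be computed. This stands as a limit on consequence. It does not make the rule correct: Section 12.3 defers detail to the SAP, the memo adds none, and so Section 12.3.1.1 and Table 7 are the only specification of the primary test.

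Second, 2.5% is nowhere stated for the primary endpoint. The only printed Type I figure is 0.05, and the Wald error stays below 5% at every total from 40 to 50. That is true, but the printed 0.05 belongs to a two-sided interval, and only its lower limit decides success.

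Third, the gap is largely discreteness. At n = 50 the choice is 32 or 33 responders, and the exact rule undershoots 2.5% by 0.86 points (2.5 − 1.64), slightly more than the Wald rule overshoots. This is fair arithmetic. For a confirmatory criterion, however, a nominal level is normally treated as a ceiling, and the conservative side costs almost nothing here.

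Fourth, totals of 40 to 50 are not the only possible ones. Section 6.7 allows replacement with the withdrawn subjects' data retained, and Section 13.10 allows termination at any time. The count of 8 in 11 describes that range only; the 3.25% at the planned total does not depend on it.

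Finally, the coverage at 83% concerns the reported limit and is not error against the 50% null. The change to Section 12.3.1.3 is for consistent reporting, because that section carries no success rule.

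**Conclusion.** The concern holds. As written, the primary criterion can declare success on 32/50, a result whose exact 95% interval includes 50%, with a one-sided error of 3.25% against an implied 2.5%. The excess depends on the final total and reaches 4.03% at 40.

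The size is small. At n = 50 the two rules disagree only at exactly 32 responders, which has probability 0.07% if the true rate is 83%. The stated power is not in question. The conclusion rests on reading normal approximation as the uncorrected Wald interval (Wilson gives the same decision at n = 50) and on inferring 2.5% from the two-sided 95% interval. No result of this study is affected. The correction is to the protocol's rule and matters if the section is reused.

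**What to change.** In Section 12.3.1.1 and Table 7, replace the normal approximation with the exact (Clopper-Pearson) two-sided 95% interval. Make the same change in Section 12.3.1.3 so that binary endpoints are reported consistently. Switching to Wilson would not cure n = 50.

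The cost is protocol wording and one SAS option. At most one more responder is needed, and none at totals of 42, 44 and 49. At n = 50 the true rate needed for 90% power rises from 71.3% to 73.1%. Power at 83% falls from 99.97% to 99.90%, and its lowest value under the exact rule for any total from 40 to 50 is 99.4% (at 41), so the power statement in Section 12.1 can stay.
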